Tuberculosis is the world's second leading cause of death from a single infectious agent in 2022, after COVID-19 [1]. In 2022, TB disease was estimated to affect 10.6 million people, from which 1.3 million died because of it, despite the WHO adoption of the End TB Strategy [1] [2]. The standardised therapy involves a treatment regimen of INH, RMP, PZA, EMB, for 2 months, then INH and RMP for at least an additional 4-7 months [3]. Even though 85% of TB cases are successfully treated, significant morbidity from treatment-related adverse events, such as hepatotoxicity, skin reactions, gastrointestinal, and neurological disorders, reduces the efficacy of therapy [4] [5] [6]. In 11% of patients receiving INH, RMP, and PZA in combination, hepatotoxicity is the most frequent adverse effect that results in drug discontinuation [5] [7] [8]. One of the most prevalent subtypes of idiosyncratic hepatotoxicity is caused by anti-TB drugs [4] [9] [10]. Numerous variables, including the features of the specific cohort, the drug regimens used, the employed threshold to define hepatotoxicity, and the monitoring and reporting procedures, influence the incidence of anti-TB drug-induced hepatotoxicity. Overall, 5%–28% of patients receiving anti-TB drugs have experienced hepatotoxicity associated with the drug [4] [10]. It is difficult to determine how many of these fit the recent international consensus definition of DILI [9]. The majority of reports have defined hepatotoxicity as an elevated level of AST or ALT that is three times the ULN when symptoms (such as abdominal pain, nausea, vomiting, unexplained fatigue, or jaundice) are present, or five times the ULN when symptoms are absent [5]. Up to 20% of patients receiving INH as monotherapy or combination therapy for TB may experience a transient, asymptomatic elevation in liver enzymes; however, it usually resolves without drug discontinuation [11] [12] [13]. ATDH may manifest as asymptomatic elevations in liver enzymes or even as fulminant liver failure [5] [14]. In accordance to these results, the most commonly observed DILI pattern is the hepatocellular one [15]. Anti-TB drugs related hepatotoxicity is of great concern not only because of its frequency but also because of its severity and outcome. The median interval between starting a course of anti-TB treatment and the onset of clinical symptoms is 16 weeks (range 6 weeks-6 months) [16] [17] [18]. Despite decades of use and a large number of patients exposed to anti-TB drugs worldwide, the pathogenesis underlying

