Patient's susceptibility to DILI during treatment with anti-TB drugs is influenced by several drug- and host-related factors [102]. The most extensively studied potential causes of INH-induced DILI are related to those mechanisms. As to drug-related factors, acetylhydrazine, which is generated by NAT2, is widely considered as a crucial INH metabolite that contributes to INH-induced DILI. Given the importance of acetylation in INH metabolism, several studies have investigated into NAT2 loss of function polymorphisms as possible risk factors for DILI. In addition, advanced age [94], female gender [86], poor nutritional status [103], HBV or HCV infection [100] [104], HIV infection [78] [105], chronic liver disease, and alcoholism are environmental, physiological, and pathological factors contributing to DILI incidence. Moreover, the influencing variables differ according to racial and geographic characteristics.

Studies conducted in China demonstrated that approximately one-third of DILI patients had no symptoms, including some cases with severe liver injury [106] [107]. It has been demonstrated that screening patients for risk factors is useful in preventing disease progression, improving the outcome of therapy, and reducing mortality. However, rapid acetylators are very common in the Chinese population, so they are characterised by a lower susceptibility to develop DILI. Our patient cohort is multi-ethnic, with a prevalence of Caucasians and so a higher frequency of slow acetylator status. For this reason, our objective is to corroborate the conclusions drawn by the previous studies through the examination of our complementary data.

Outcome measures and assessments

The primary outcome is to determine the association between risk factors (drug- and host-related factors) and the incidence of DILI.

The primary outcome measures are the occurrence of anti-TB DILI (number of participants with DILI), which was defined by: 1) AST or ALT level > 5 times the ULN in patients with absence of symptoms or with total BIL level > 2 times the ULN, or 2) AST or ALT level > 3 times the ULN and total BIL level > 3 times the ULN in patients who show symptoms compatible with hepatitis.

The secondary outcome is to evaluate the characteristics of patients who first experienced anti-TB DILI. The secondary outcome measures are the prevalence of early hepatotoxicity experience.

Methods

Study design

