This is a retrospective observational study, no profit, to determine environmental, physiological, and pathological factors associated with the incidence of DILI during anti-TB treatment. Data collected from patients with confirmed tuberculosis, enrolled at the Department of Infectious Diseases of Luigi Sacco Hospital in Milan, Italy, between July 2020 and September 2023, will be analysed. Subjects were all followed up as outpatients at Tuberculosis Clinic at Luigi Sacco Hospital, some of them with previous inward stays at various hospitals in the Lombardy Region.

Study population

The following are the inclusion criteria: 1) adult patients (>18 years), 2) patient who received standard initial therapy including INH (5mg/kg), RMP (10mg/kg), and PZA (25mg/kg) for patients with active TB disease, 3) treatment with first line anti-TB drugs, including rifampicin and isoniazid for patients with latent TBI, 4) normal serum ALT and bilirubin levels, no symptoms related to abnormal liver function prior to anti-TB drug treatment and 5) informed consent. Patients with any of the following conditions are excluded from the study: 1) liver dysfunction, including biliary origin, before anti-TB therapy, 2) patients receiving non-standard treatment regimen initially (e.g., patients with severe pulmonary or extrapulmonary TB receiving large doses or more than four anti-TB drugs), 3) modified treatment regimen due to drug resistance or intolerance excluding first line anti-TB drugs, 4) lactation or pregnancy, 5) concomitant use of hepatotoxic drugs, 6) abnormal hepatic function on laboratory testing before anti-TB, 7) disease that was resistant to INH at the start of treatment or 8) patients refusing to sign informed consent.

The participants were given standard anti-TB treatment in line with international guidelines (RMP 10 mg/kg, INH 5 mg/kg), primarily administered orally, although intravenous administration was

employed for inpatients as needed, and modified to oral administration as soon as possible. The other drugs of the standard regimen included standard daily doses of PZA (15-30 mg/kg) and EMB (15-20 mg/kg).

Data collection

Data that will be collected include clinical, biochemical, and genotyping findings that are typically used in clinical practice to manage and monitor tuberculotic patients at Luigi Sacco Hospital. The complete list of parameters (host- and drug-related factors) is provided below:

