- Clinical data: age, weight, height, gender, ethnicity, hepatotoxicity or alcoholism, duration of anti-TB treatment, tuberculosis site (pulmonary or extra), adverse event, concomitant infection (HIV, HAV, HCV, HBV), past medical history, concomitant drugs. Patient's nutritional status was reported as BMI, which was calculated based on height and body weight;
- Biochemical data: ALT, AST, GGT and BIL;
- Laboratory data: NAT2 acetylator status. The acetylation status of patients will be assigned like as suggested by earlier research:
 - rapid acetylator: NAT2*4 is a wild-type allele (defined by absence of slow alleles);
 - intermediate acetylator status: carry one copy of NAT2*4 and one defective variant allele (NAT2*5, *6, *7, and *14);
 - slow acetylator: two copies of slow variant allele (NAT2*5, *6, *7, and *14).

Statistical analysis

Sample size calculation

[figure not shown]
We are planning a study of matched sets of cases and controls with 2 matched controls per case. Prior data indicate that the probability of exposure among controls is 50%, and the correlation coefficient for exposure between matched cases and controls is -0.2 [10] [108] [109] [110] [111]. If the true odds ratio for disease in exposed subjects relative to unexposed subjects is 3, we will need to study 40 case patients with 80 matched controls to be able to reject the null hypothesis that this

odds ratio equals 1 with a power of 80%, assuming that the Type I error probability associated with the test of this null hypothesis is 5%.

[figure not shown]
Parameters: Exposure in cases = 75%; Exposure in controls = 50%

Absolute difference = 25%; Relative difference = 50%; Odds ratio = 3

Sample sizes across range of OR and control exposure, with inputted values:

Number of cases required varying ratio of controls per case, other inputs constant:

We will use a nested case-control study design that takes into account time of events occurrence in sampling of controls. For each case, one or more controls are selected from the risk set at the time in which the event of interest occurred in the case. The risk set means the set of all individuals that are still “events-free” and not censored. Therefore, they are still included in the study at that time, thus, eligible to experience the event now observed in the case. As a consequence, individuals can

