be sampled as controls for more than one case and, in turn, individuals sampled as controls may subsequently become cases. Cases and controls will be matched according to baseline variables, including age, sex, and BMI, and then conditional regression analysis (a type of matched statistical analysis) will be performed to draw associations.

Data management

All data are retrieved from the patient's medical record. Variables will be entered into the eCRF by site staff, who will be trained on how to use the eCRFs and capture the data required by the protocol. The eCRF is an electronic data entry media and should not constitute the original (or source) medical record. Data derived from source documents and reported in the eCRFs should be consistent with the source documents, or the discrepancies should be explained in these source documents. The investigator must complete the eCRF for each participant. The investigator's signature on the eCRF will attest to their accuracy and completeness.

Data collected from each participant will be anonymized: each subject will be assigned a unique code so that only the investigator will be able to identify the subject. The file associating the participant's code with their identifying data will be stored separately on a password protected computer. The study database will be password protected and uploaded to a computer that is also password protected and accessible only to study personnel designated by PI. Identification of the data will be done in such a way that individuals accessing the database will not be able to trace the identity of the subjects in any way.

The study will involve statistical calculations on collected data using literature standard methods to identify and correlate variables (Chi-square, Fisher's exact, Mann-Whitney U-test, conditional regression). The results will be published in medical journals and presented at conferences. Study data will be retained for 7 years starting from the study's conclusion. Data processing will be done in strict compliance with GDPR and any applicable national legislation.

Potential Benefit of the Study

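### Liver-test frequency may differ by NAT2 status or other risk factors; control sampling does not allow for this in symptom-free DILI, and the listed data could not reveal it

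*Protocol*

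**What the plan says.** - **Case definition** (Outcome measures and assessments). The first route is "AST or ALT level > 5 times the ULN in patients with absence of symptoms or with total BIL level > 2 times the ULN". The second needs AST or ALT above 3 times ULN and total bilirubin above 3 times ULN in patients with symptoms of hepatitis.
- **Source of the tests** (Study design; Data management). The study is retrospective, and "All data are retrieved from the patient's medical record". No liver-test schedule or minimum number of tests is stated.
- **Use of genotype in care** (Data collection). The items collected include "genotyping findings that are typically used in clinical practice to manage and monitor tuberculotic patients at Luigi Sacco Hospital". What is presented as the full list of parameters names ALT, AST, GGT, bilirubin and NAT2 acetylator status. It names neither panel dates nor the date on which the NAT2 result became known.
- **Control sampling** (Statistical analysis). The sentence that begins "The risk set means the set of all individuals that are still" asks only that a control be free of the event and uncensored. The matching variables named are age, sex and BMI.
- **Background figures.** Rationale and Aims cites Chinese studies in which "approximately one-third of DILI patients had no symptoms". The introduction includes, among the things that affect measured frequency, "the monitoring and reporting procedures, influence the incidence of anti-TB drug-induced hepatotoxicity".

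**The concern.** A symptom-free episode becomes a case only if a panel is drawn while the enzymes are raised. If no panel is drawn, the patient stays event-free on paper and can be sampled as a control. This does little harm when everyone is tested equally often. It distorts the odds ratio when testing intensity goes with the exposure.

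The protocol gives reason to think that it might. Genotyping is described as part of how patients are managed and monitored, and screening for risk factors is endorsed (Rationale and Aims; Potential Benefit of the Study). Slow acetylators, patients with HIV or viral hepatitis, and drinkers may therefore have been tested more often. A raised NAT2 odds ratio could then combine biology with closer surveillance. Nothing in the sampling rule or the named matching variables separates the two, and without dated panels no later analysis could.

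**Working it through.** **1. The plan's own figure.** Inputs from Sample size calculation: control exposure p0 = 0.50, odds ratio ψ = 3, correlation −0.2, M = 2 controls per case, power 80%, type I error 5% (taken as two-sided). Dupont's formula for matched sets gives:
- case exposure p1 = 0.5 × 3 / (1 + 0.5 × 2) = 0.75; covariance = −0.2 × √(0.75 × 0.25 × 0.5 × 0.5) = −0.0433;
- chance that a control is exposed: (0.375 − 0.0433)/0.75 = 0.4423 if the case is exposed, and (0.125 + 0.0433)/0.25 = 0.6732 if not;
- chance that a set of three has exactly one exposed member: t1 = 0.75 × 0.5577² + 0.25 × 2 × 0.6732 × 0.3268 = 0.3433; exactly two: t2 = 0.75 × 2 × 0.4423 × 0.5577 + 0.25 × 0.6732² = 0.4833;
- expected exposed cases per set: t1/3 + 2·t2/3 = 0.4366 at ψ = 1, and 3·t1/5 + 6·t2/7 = 0.6202 at ψ = 3. The variances are (2/9)(t1 + t2) = 0.1837 and 6·t1/25 + 6·t2/49 = 0.1416;
- n = (0.8416 × √0.1416 + 1.96 × √0.1837)² / (0.6202 − 0.4366)² = 39.69, so 40 cases and 80 controls, as stated. Power at 40 cases is 80.3%.

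**2. Size of the distortion.** Let a be the symptom-free share of true DILI and d the chance that such an episode is found in the less-watched group. Assume no true effect, that all symptom-free episodes are found in the watched group, and that symptomatic episodes are always tested. Then

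spurious ratio = 1 / (1 − a + a·d).

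The share a = 1/3 is the protocol's. The values of d are assumptions, because the protocol gives none. The last column repeats step 1 at 40 cases with ψ set to the spurious ratio. It is the chance of a false significant result in the harmful direction.

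| d | Spurious ratio | False harmful result |
|---|---|---|
| 1.00 | 1.00 | 2.5% |
| 0.75 | 1/0.9167 = 1.09 | 4.2% |
| 0.50 | 1/0.8333 = 1.20 | 7.1% |
| 0.25 | 1/0.75 = 1.33 | 11.7% |
| 0 (limit) | 1/0.6667 = 1.50 | 18.8% |

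**3. Against the effects of interest.** The lowest NAT2 odds ratio in the range cited under Isoniazid is 1.59. On the log scale a spurious 1.20 is ln 1.20 / ln 1.59 = 39% of that effect, and 1.33 is 62%. A true ratio of 3 would appear as at most 3 × 1.5 = 4.5, and a true ratio of 0.5 as at most 0.75.

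**4. Which control rule removes it.** Suppose that d is also the chance of a panel in a window around the index day.
- *Panel required of every control.* The watched group is over-represented by 1/(1 − a + a·d) among cases and by 1/d among controls. The null odds ratio is d/(1 − a + a·d): 0.75/0.9167 = 0.82, 0.50/0.8333 = 0.60 and 0.25/0.75 = 0.33. A modest upward bias becomes a larger downward one.
- *Panel required only in sets with a symptom-free case.* Cases and controls are both over-represented by 1/d, so the ratio is 1. In symptom-prompted sets the planned risk set already gives 1.

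**The case against.** The strongest reply is that differential testing is conjecture. No part of the protocol says that liver tests were ordered more often by genotype, HIV, hepatitis or alcohol. Study design says that all subjects were followed at one outpatient clinic. The sentence on genotyping describes three kinds of data together. It does not say that genotype set test frequency, or that results were back before the event. This stands, and it is why the point is conditional. It does not remove the point, because uniform testing is not stated either and could not be checked from the listed data.

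A reader might infer that closely watched groups will show more DILI whatever their true risk. The documents do not support that: with equal testing the factor is 1.00, and at the one-third share it stops at 1.5. A reader might also infer that symptom-free cases form the majority here, because the symptomatic route asks for bilirubin above 3 times ULN. That overlooks the first route. As worded, it also admits AST or ALT above 5 times ULN with bilirubin above 2 times ULN, so a symptomatic patient can qualify without reaching 3 times.

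Two further replies have weight. Covariates and sensitivity analyses are commonly left to the SAP, so their absence is no fault. The data list, however, is fixed in this document. Contamination of controls by missed cases is also small: with DILI in 5% to 28% of patients (introduction) and one-third symptom-free, it is at most about 2% to 9% even if every silent case were missed. The bias comes mainly from which cases are found.

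**Conclusion.** The point holds as a conditional design weakness that is cheap to repair. Detection of symptom-free DILI depends on testing, testing may depend on the exposures under study, and the protocol neither samples for this nor lists the data that would show it.

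If testing was uniform, the bias is nil. Otherwise the spurious ratio is 1.09 to 1.33 for assumed detection of 75% to 25% against 100%, with a ceiling of 1.5. That is enough to create or inflate a modest association, but not to produce the planned odds ratio of 3.

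The ceiling rests on two assumptions: that symptomatic episodes are always tested, and that the one-third share from other cohorts applies in Milan. In general it is 1/(1 − a), so a larger silent share would raise it. To reach 3 from nothing would take a = 2/3 with no silent case found in the less-watched group, and no figure in the protocol supports that.

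**What to change.** 1. Add to the list under Data collection the dates of all ALT, AST and bilirubin panels and the date on which the NAT2 result reached the treating team. Do this before abstraction starts, since the study is planned to last three months.
2. Report panel frequency by NAT2 group and by the other main risk factors. If it is similar, the concern falls away.
3. In the risk-set definition, for sets whose case was symptom-free, require controls to have a below-threshold panel within a fixed window of the case's treatment day (for example 14 days either side). Keep the planned risk set for symptom-prompted cases, for the reason in step 4 of the working.
4. Add two sensitivity analyses: one limited to cases with symptoms or raised bilirubin, and one limited to matched sets in which no NAT2 result was known before the index day.

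The cost is a little more abstraction from the laboratory system, with no change to patient care. Fewer controls will be eligible for silent cases, and the restricted analyses will be less precise than the main one.

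### Active-TB and latent-TBI patients share one risk set, but the listed data fields include neither active/latent status nor initial regimen, so confounding by treatment group could not be checked or controlled from them

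*Protocol*

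**What the plan says.** - **Two treatment groups (Protocol, Study population).** Criterion 2 admits patients on "standard initial therapy including INH (5mg/kg), RMP (10mg/kg), and PZA (25mg/kg) for patients with active TB disease". Criterion 3 admits those on "treatment with first line anti-TB drugs, including rifampicin and isoniazid for patients with latent TBI"; it neither names nor excludes PZA.
- **A conflicting description (Protocol, Study design).** The analysed data are described as "Data collected from patients with confirmed tuberculosis", which does not fit criterion 3.
- **One risk set (Protocol, Sample size calculation).** "The risk set means the set of all individuals that are still" free of the event and not censored. It is not divided by active/latent status or regimen.
- **Matching (Protocol, Statistical analysis).** "Cases and controls will be matched according to baseline variables, including age, sex, and BMI". The list is open, but neither active/latent status nor regimen is named. Conditional regression follows.
- **Data fields (Protocol, Data collection).** The list is introduced as "The complete list of parameters (host- and drug-related factors) is provided below". The items nearest to treatment group are "duration of anti-TB treatment, tuberculosis site (pulmonary or extra), adverse event", followed by concomitant infection, past medical history and concomitant drugs. Active/latent status and the anti-TB drugs received are absent.
- **Source (Protocol, Data management).** "All data are retrieved from the patient's medical record".

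**The concern.** The protocol's opening background counts the regimen used among the things that influence the incidence of hepatotoxicity, and the section Factors Associated with Drug names PZA as hepatotoxic alongside INH and RMP. The study then pools a group whose regimen includes PZA with a group for which PZA is not required, and leaves treatment group off a field list that it calls complete.

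If active patients have more DILI than latent patients, they will be over-represented among cases compared with controls drawn from the pooled risk set. A host factor that is more common in one group will then show an association with DILI that partly reflects treatment group. A factor equally common in both groups will not. From the listed fields an analyst could neither tell which situation applies nor correct for it. A later SAP can choose matching factors and covariates, but only from what has been collected.

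**Working it through.** **1. The plan's own figure.** The matched case-control formula of Dupont, with 2 controls per case, control exposure 50%, OR 3, correlation -0.2, two-sided 5% and power 80%, gives 39.69, so 40 cases and 80 controls. This reproduces the protocol. The present point does not dispute it.

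**2. Can a listed field stand in for treatment group?**
- Treatment duration: DILI may itself cut treatment short, so duration is a poor adjustment variable.
- Tuberculosis site: the two options are pulmonary or extrapulmonary, with no latent category. A blank might mean latent infection or missing data, and no coding rule is given.
- Concomitant drugs: a separate item, not described as the anti-TB regimen.

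None is an adequate substitute.

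**3. How large could the bias be?** The protocol gives no active/latent mix, no DILI rate by group and no prevalence of any host factor by group. All inputs here are therefore assumptions:
- f = share of the cohort with active TB: 0.3, 0.5, 0.7, 0.9. The last value reflects the study-design wording.
- RR = DILI rate in active over latent patients: 2.
- pa, pl = prevalence of the factor in active and latent patients. The factor has no true effect.
- Risk sets have the same mix as the cohort, and matching on age, sex and BMI does not alter it.

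Formulas:
- share of cases that are active: s = f·RR / (f·RR + 1 − f)
- exposure in cases: c = s·pa + (1 − s)·pl
- exposure in controls: d = f·pa + (1 − f)·pl
- OR = [c/(1 − c)] / [d/(1 − d)]

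Worked case, f = 0.5, pa/pl = 0.50/0.25: s = 1.0/1.5 = 0.667; c = 0.667 × 0.50 + 0.333 × 0.25 = 0.4167; d = 0.375; OR = 0.7143/0.6000 = 1.19.

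| pa/pl | f = 0.3 | f = 0.5 | f = 0.7 | f = 0.9 |
|---|---|---|---|---|
| 0.50/0.50 | 1.000 | 1.000 | 1.000 | 1.000 |
| 0.50/0.40 | 1.068 | 1.069 | 1.051 | 1.019 |
| 0.50/0.25 | 1.196 | 1.190 | 1.134 | 1.049 |
| 0.40/0.50 (reversed) | 0.937 | 0.935 | 0.951 | 0.981 |
| 0.25/0.50 (reversed) | 0.846 | 0.833 | 0.865 | 0.942 |

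**4. False-positive rate.** Simulation of 40 sets of one case and two controls, matched score test, two-sided 5%, 40,000 runs per cell. Rejection rates in % at f = 0.3, 0.5, 0.7, 0.9:
- 0.50/0.50: 5.0, 4.9, 5.1, 5.0
- 0.50/0.40: 5.2, 5.4, 5.3, 5.1
- 0.50/0.25: 7.6, 7.7, 6.2, 5.0
- 0.40/0.50: 5.3, 5.4, 5.2, 5.1
- 0.25/0.50: 6.8, 6.9, 5.8, 4.7

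Drawing each control from its case's own treatment group brings every one of these cells to between 4.7% and 5.2%.

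**The case against.** The strongest reply is that nothing is lost. The study is retrospective, all data come from the chart, the investigator holds the link between code and patient, and criteria 2 and 3 cannot be applied without knowing status and drugs. This stands. A reader might infer that the adjustment is impossible for good; the documents support only that the listed fields do not allow it.

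Second, the latent group may be small. The study-design wording points to a mostly active cohort, and at 90% active the bias nearly vanishes. This also stands, and it makes the conflict with criterion 3 part of the point rather than a matter of wording.

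Third, the matching list is open, and covariates may be set in a SAP that is not at hand. True, but a field must be collected before it can be used, and the field list is fixed in the protocol.

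Fourth, no passage reports an imbalance. NAT2, which the protocol stresses, is an inherited genotype, and nothing suggests that it differs between the groups. That is correct, and at equal prevalence the bias is nil.

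A reader might also derive a rate ratio of about 4 by dividing the background's 11% by its 2.7%. The first figure is hepatotoxicity leading to discontinuation on INH, RMP and PZA. The second is clinical hepatitis in adults on INH and rifampicin, not stated to have latent infection. Endpoints and populations differ, so the ratio is not used here.

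**Conclusion.** The point holds as a gap in the field list. Followed as written, the protocol yields a dataset on which confounding by treatment group can be neither examined nor controlled, although the protocol itself regards regimen as a determinant of hepatotoxicity.

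The size of any bias is unknown. Under an assumed rate ratio of 2 and 30% to 90% of the cohort active, the OR for a null factor is 1.00 at equal prevalence, about 1.02 to 1.07 at 50%/40% and about 1.05 to 1.20 at 50%/25%, with false-positive rates of about 5% to 8%. Reversed imbalances push the OR below 1 by a similar degree. These are modest beside the OR of 3 that the design targets. A larger rate ratio would enlarge them, but the documents give no usable value.

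Two stronger inferences are not supported. The documents do not show that the planned estimates are biased, since no imbalance between the groups is documented. Nor do they make a comparison of regimens an aim: the primary outcome covers drug-related factors, but Rationale and Aims explains these through INH metabolism and NAT2, which is collected. This is a cheap improvement to make before data extraction, not a fatal flaw.

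**What to change.** 1. In Data collection, add active/latent status and the initial anti-TB drugs received, both taken from the medical record.
2. Sample each control from its case's treatment group, or adjust for treatment group in the conditional regression. Adjust rather than match if the regimen effect is itself of interest, because matching on it would prevent its estimation.
3. Reconcile the reference to confirmed tuberculosis in Study design with the latent-TBI criterion in Study population, and state which patients are analysed. This decides how much the point matters.

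The cost is one or two eCRF fields already consulted for eligibility and one sentence on sampling or adjustment. The downside is smaller risk sets if sampling is within group, or one extra model term with about 40 cases.

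### The sample-size inputs conflict: 75%/50% exposure and an odds ratio of 3 agree only at zero correlation, where 40 cases and 80 controls give about 76% power, not 80%

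*Protocol*

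**What the plan says.** The calculation stands in the Protocol under Statistical analysis, Sample size calculation. It plans matched sets with two controls per case.

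- Control exposure: "Prior data indicate that the probability of exposure among controls is 50" per cent.
- Correlation: "the correlation coefficient for exposure between matched cases and controls is -0.2 [10] [108] [109] [110] [111".
- Effect: "If the true odds ratio for disease in exposed subjects relative to unexposed subjects is 3".
- Result: "we will need to study 40 case patients with 80 matched controls to be able to reject the null hypothesis", with 80% power and 5% type I error.

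A parameter list then adds "Parameters: Exposure in cases = 75%; Exposure in controls = 50" per cent, and "Absolute difference = 25%; Relative difference = 50%; Odds ratio = 3".

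The same section describes a nested case-control design: "For each case, one or more controls are selected from the risk set at the time in which the event of interest occurred". On matching it says: "Cases and controls will be matched according to baseline variables, including age, sex, and BMI". The analysis is to be conditional regression.

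The section does not name the exposure, say which of the five references supplied -0.2, explain the negative sign, or say whether the odds ratio of 3 is marginal or within-set.

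**The concern.** Conditional regression estimates the within-set odds ratio, which is driven by discordant case-control pairs. Once the two exposure percentages and the correlation are fixed, that odds ratio is fixed too and cannot be chosen separately. The Protocol prints all four values, so they can be tested against one another.

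The sign is a second difficulty. Matching on age, sex and BMI would be expected to make cases and their controls more alike in exposure, or leave them unrelated. With the odds ratio held at 3, a negative correlation makes the required sample smaller than zero correlation would.

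At stake is the only justification given for 40 cases and 80 controls. A reader of a null result would rely on the stated 80%.

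**Working it through.** **Inputs (all from Sample size calculation).** M = 2 controls per case; control exposure p0 = 0.50; case exposure p1 = 0.75; odds ratio ψ = 3; correlation φ = -0.2; power 80%; type I error 5%. Sidedness is not stated. I take it as two-sided, because a one-sided test with these inputs gives 31.0 cases, not 40.

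**Formula (Dupont, matched case-control, M = 2).** With q = 1 - p:

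- c = φ·√(p1·q1·p0·q0); p+ = (p1·p0 + c)/p1; p- = (q1·p0 - c)/q1
- t_m = p1·C(2, m-1)·p+^(m-1)·(1-p+)^(3-m) + q1·C(2, m)·p-^m·(1-p-)^(2-m), for m = 1, 2
- e_ψ = Σ m·t_m·ψ/(mψ+3-m); v_ψ = Σ m·t_m·ψ·(3-m)/(mψ+3-m)²
- n = (0.8416·√v_ψ + 1.96·√v_1)² / (e_ψ - e_1)²
- power at N sets = Φ[((e_ψ - e_1)·√N - 1.96·√v_1)/√v_ψ]

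**Step 1: reproduce the Protocol's figure.** c = -0.2 × √(0.75×0.25×0.5×0.5) = -0.0433, so p+ = 0.4423 and p- = 0.6732. Then t_1 = 0.3433, t_2 = 0.4833; e_1 = 0.4366, e_3 = 0.6202; v_1 = 0.1837, v_3 = 0.1416. This gives n = (0.3167 + 0.8401)²/0.1836² = 39.7, so 40 cases, with 80.3% power. The stated figure reproduces.

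**Step 2: test whether the inputs agree.** Let P10 be the probability that the case is exposed and the control is not, P01 the reverse, and P11 both exposed.

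- The margins force P10 - P01 = 0.75 - 0.50 = 0.25.
- A within-set odds ratio of 3 forces P10 = 3·P01, so P01 = 0.125 and P10 = 0.375.
- Then P11 = 0.50 - 0.125 = 0.375 = 0.75 × 0.50. That is independence, so φ = 0 exactly.
- With φ = -0.2 instead, P11 = 0.375 - 0.0433 = 0.3317, P10 = 0.4183 and P01 = 0.1683. The odds ratio is 0.4183/0.1683 = 2.49, not 3.
- To keep both 3 and -0.2, case exposure must be 79.1% (P10 = 0.436, P01 = 0.1453).

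**Step 3: power at 40/80 under each reconciliation.**

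| Input given up | Case exposure | Odds ratio | φ | Cases for 80% | Power, formula | Power, simulated |
|---|---|---|---|---|---|---|
| none (as printed, not coherent) | 75% | 3 | -0.2 | 39.7 → 40 | 80.3% | – |
| correlation | 75% | 3 | 0 | 43.7 → 44 | 76.1% | about 76% |
| case exposure | 79.1% | 3 | -0.2 | 40.2 → 41 | 79.8% | 83.1% |
| odds ratio | 75% | 2.49 | -0.2 | 56.1 → 57 | 64.6% | 70.0% |

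For the zero-correlation row, t_1 = 0.3125, t_2 = 0.4375, e_3 - e_1 = 0.5625 - 0.3958 = 0.1667, v_1 = 0.1667 and v_3 = 0.1286. So power = Φ[(0.1667×6.325 - 1.96×0.4082)/0.3586] = Φ(0.71), about 76%. The simulated column is the conditional score test with controls independent given the case's exposure. At zero correlation the likelihood-ratio and Wald tests simulate at 76.9% and 74.7%. At 44 sets the formula and the score-test simulation both give about 80%.

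**Step 4: the sign.** Suppose a set's controls are exposed with probability p and all sets share odds ratio ψ. The case is then exposed with probability ψp/(1 - p + ψp), which rises with p. Given the set, case and control exposures are independent, so their overall covariance is that of p with an increasing function of p. It is zero or positive. By the same formula with the odds ratio held at 3, power at 40/80 is 73.1% at +0.1 (47 cases needed) and 69.1% at +0.2 (51 cases).

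**The case against.** The best defence is that 40/80 is no miscalculation. The sentence that states the power uses 50%, -0.2 and an odds ratio of 3, and the matched formula returns 40. The 75% appears only in the parameter list and is what 50% and an odds ratio of 3 give without matching (1.5/(1.5 + 0.5)). It may be derived output. If it is moved to 79.1%, power stays at about 80%. The five sources cannot be read here, and choosing zero because the other figures agree there is not evidence about the correlation.

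Much of this stands. The calculation does reproduce, and 76% applies when the correlation is the input given up. But keeping -0.2 meets the sign argument: under the common within-set odds ratio that conditional regression normally assumes, the correlation cannot be negative. By printed title, only reference [111] is a matched case-control study.

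It can also be said that a positive correlation need not lower power. With 75% and 50% held, power rises to 82.0% at +0.1 and 87.9% at +0.2. Those figures need within-set odds ratios of 3.42 and 4.06, which the Protocol does not assume.

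Finally, the consequence is small. An odds ratio of 3.17 would restore 80% at zero correlation, and the Isoniazid background section reports odds ratios for slow acetylators from 1.59 to 6.42, a far wider uncertainty. The section also announces tables over a range of odds ratios and control exposures; their contents are not visible and could not be checked.

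**Conclusion.** The concern holds. 75%, 50%, a within-set odds ratio of 3 and a correlation of -0.2 are mutually incompatible; this is exact algebra. The stated 80% is recovered only by holding the odds ratio at 3, keeping a correlation of implausible sign and setting aside the printed 75%.

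With the odds ratio held at 3 and a correlation of zero or above, power at 40/80 is at most about 76%. The shortfall at zero is 80 - 76 = 4 points, or 44 - 40 = 4 cases. If the printed percentages and -0.2 are kept instead, power is 65% by formula and 70% by simulation.

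The conclusion rests on a two-sided 5% test, two controls per case, 50% control exposure and a common within-set odds ratio. The incompatibility is certain. The choice of zero follows from the sign argument and from agreement with the other printed inputs, not from outside data. Only a planning input and the printed power are affected.

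**What to change.** In Sample size calculation, state which odds ratio is meant, set the correlation to 0 and restate the power. Suggested text:

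> The odds ratio of 3 is the within-set odds ratio. Exposure among controls is taken as 50% and the correlation of exposure between matched cases and controls as 0, the value at which 75% case exposure, 50% control exposure and an odds ratio of 3 agree. With 40 cases and 80 matched controls, power is about 76% at a two-sided 5% level; 44 cases with 88 controls would be needed for 80%.

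An optional further sentence could report that, with the within-set odds ratio held at 3, power is about 73% at a correlation of +0.1 and 69% at +0.2.

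If the cited sources do justify -0.2, keep it, but name the exposure and the source, explain the sign, and change 75% to about 79% together with the absolute and relative differences printed beside it.

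The cost is wording, and printing 76% in place of 80%. Study design gives a data window of July 2020 to September 2023, which has closed, so reaching 44 cases may not be possible. The restatement does not require it.
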